The *Parental Expectations Questionnaire*(H. M. Chiang, Cheung, Hickson, Xiang, & Tsai, 2012) will be completed by parents and was developed from the National Longitudinal Transition Study-2 to assess parental expectations in the areas of education, postsecondary school completion, and independence. Each item is scored on a 4-point Likert scale and the raw score will explore the relationship between expectations and participation in the intervention.

The **Family Quality of Life (FQOL) scale**(Hoffman, Marquis, Poston, Summers, & Turnbull, 2006) will be completed by parents and has 5 domains that assess family interaction, parenting, emotional well-being, physical/material well-being, and disability related support. Each of the 25 items is scored on a 5-point Likert scale and the raw score on each domain will explore the relationship between family quality of life and participation in the intervention.

The Community Integration Scale is a 33-item measure that documents a person's involvement in their community. There is a parent version for their child, and a self-report version.

Child Concentration Inventory, Second Edition (CCI-2). The CCI-2 (Becker, 2015) is a child-report measure of SCT symptoms. The CCI-2 consists of 16 items that are rated on a four-point scale (0 = never, 1 = sometimes, 2 = often, 3 = always). There is evidence supporting the reliability and validity of the CCI-2 in children and adolescence (Sáez, Servera, Burns, & Becker, under review).

Child and Adolescent Behavior Inventory (CABI). The CABI SCT module was derived from a meta-analysis which examined the stability and reliability of SCT items derived from various measures (Becker et al., 2016). Parents will complete the CABI (Burns, Lee, Servera, McBurnett, & Becke, 2015) SCT module. Recent studies support the reliability and validity of the CABI (Becker, Burns, Schmitt, Epstein, & Tamm, 2017; Sáez, Servera, Becker, & Burns, 2018).

The Social Skills Improvement System (SSIS). The SSIS (Gresham, 2008) is a parent and self-report measure that assesses social skills (i.e., communication, responsibility, self-control, cooperation), competing problem behaviors (e.g., externalizing, internalizing, bullying), and academic competence (e.g., motivation to learn). Raw scores and standard scores will be utilized to explore the relationship between social skills and participation in the intervention.

It will be completed by parents and adolescents at the baseline, post-treatment, and 6-month followup assessment visits.

Friendship Qualities Scale (FQS). The Friendship Qualities Scale (Bukowski, Hoza, & Boivin, 1994) is a teen self-report measure that assesses the quality of best friendships. It uses a Likert scale on each of the 23 items, from 1 to 5. Teens are instructed to identify their best friend and keep this friendship in mind when completing this measure. It has 5 subscales: companionship, closeness, help, security, and conflict.

Test of Adolescent Social Skills Knowledge (TASSK). The Test of Adolescent Social Skills Knowledge (Laugeson, Frankel, Mogil, & Dillon, 2009) is a 26-item criterion-referenced test developed for PEERS to assess the teen's knowledge about the specific social skills taught during the intervention. Teens are presented with sentence stems and asked to choose the best option from two possible answers.

Quality of Play Questionnaire (QPQ). The Quality of Play Questionnaire (Frankel & Mintz, 2008) consists of 12 items, both teen and parent versions, to assess the frequency of get-togethers with peers over the previous month. It also assesses the level of conflict during these get togethers.

Follow Up Young Adult Survey Questions. This survey was created by the study P.I. and is conducted interview-style by study staff. It is compilation of questions obtained from the NLTS-2 WAVE 5 Parent and Young Adult Forms, which are free to the public. The purpose of the measure is to examine how participation in Surviving and Thriving in the Real World daily living skills intervention affects future outcomes.

Outcomes Survey. This survey, completed by parents via Redcap survey, assesses their child's current status in education, work, independent living, social connectedness, and daily living skills.

STRW Intervention Group:

The STRW intervention consists of 14 weekly concurrent adolescent and parent group sessions. The DLS to be targeted in the intervention include: *Morning Routine* (i.e., completing a morning personal hygiene routine); Laundry (i.e., sorting clothing, using a washing machine and dryer, and folding and putting clothes away); Kitchen/Cooking (i.e., cooking items in the microwave, oven, and stove, safe kitchen practices, cleaning up the kitchen after cooking, and grocery shopping); Self-Management (i.e., managing worry and stress related to learning DLS and transitioning to adulthood); and *Money* Management (i.e., using money to purchase items, evaluating the quality and price of items, understanding and using a checking and savings account, and budgeting money to cover expenses). The above targeted skills are based on the preliminary studies conducted by [name] on common DLS deficits in high functioning adolescents with ASD(Duncan, Ruble, Meinzen-Derr, Thomas, & Stark, in press; Duncan et al., 2014). Several evidence-based strategies will be utilized to help adolescents acquire specific DLS in session and then generalize these skills to the home and the community. Specifically, in adolescent group sessions, visual strategies such as creating a task analysis and checklist of steps (e.g., the steps involved in doing laundry) are used to increase skill acquisition. Technology such as video modeling (e.g., creating a movie of one completing their personal hygiene routine that can be watched on their computer or phone) or apps for smart phones (e.g., money management app, grocery store app, cooking app with videos of recipes) are also used because these have been shown to be an effective way to understand and learn targeted skills in other areas of functioning and increase motivation for learning new skills(Burton, Anderson, Prater, & Dyches, 2013; Satriale, Chance, & Nepo, 2009) in individuals with ASD. Parent participants will receive instruction on how to utilize evidence-based strategies to teach and generalize DLS for adolescents with ASD including a behavior contract, task analysis, chaining, modeling, reinforcement, rewarding reasonable attempts, prompting, prompt fading, generalization, incorporating special interests, visual strategies, self-management, video modeling, and technology(Hume et al., 2014;

National Autism Center, 2009; Wong et al., 2015). Due to COVID-19, an undetermined number of sessions will be conducted via telehealth using a HIPAA compliant version of Zoom.

STRW In-Person Sessions: The STRW parent sessions will be facilitated by the PI. The STRW adolescent sessions will be facilitated by a psychology post-doctoral fellow and graduate student trainees (e.g., in the fields of psychology and occupational therapy) recruited from the Leadership Education in Neurodevelopmental Disabilities (LEND) training program at CCHMC (see letter of support for additional information).

Group Sessions. Each group session lasts 90 minutes and consists of four main components: (1) Overview of session activities; (2) Updates from group members on progress towards DLS goals being targeted and weekly homework assignments; (3) Divide into separate parent and adolescent groups to work on session-specific content; and (4) Reconvene as a group to summarize and share the activities that were done during the session and discuss homework assignments targeting the DLS goals for the week. Weekly homework assignments will be given to the adolescent to encourage acquisition, maintenance, and generalization of skills to the home and/or community (e.g., do laundry at home, purchase items at a grocery store using a pre-defined budget). Completion of homework assignments will be tracked at each session via parent and adolescent report. In addition, parents will be contacted by email or text message (parent preference) each day to track completion of homework assignments. Throughout each session, the therapists will facilitate the development of a behavior contract that specifies when the newly taught DLS will be practiced and the contingent reward that the parent will provide (see Figure 3 for an example of a completed behavior contract). At the end of each session, parent and adolescent pairs will complete feasibility, acceptability, and satisfaction surveys.

Adolescent Group Sessions.

Each week one DLS will be targeted. Through didactics and demonstration, therapists will teach and model how to break down a target skill into manageable steps and then work towards completing each step using evidence-based strategies that have been shown to be effective for adolescents with ASD(Hume et al., 2014; National Autism Center, 2009; Wong et al., 2015). For example, for the session targeting cooking on the stovetop, therapists will utilize visual strategies (e.g., following a recipe with both written directions and pictures of each step), technology (e.g., viewing a video of how to cook scrambled eggs using a phone app that has both recipes and accompanying videos that demonstrate how to cook the recipe), and direct instruction and feedback as each adolescent participant prepares, cooks 1-2 items, and cleans up the kitchen area. Adolescents will work with therapists as a group to learn and practice the skills in each session. While not directly targeted, appropriate social skills will be modeled (e.g., listening to others, respecting others' opinions, offering appropriate advice to other teens) and discussed when relevant (e.g., tips for interacting with cashiers when grocery shopping, how to effectively negotiate with parents using the behavior contract). The importance of acquiring DLS will be discussed in each session to increase understanding and foster motivation.

Parent Group Sessions. Each week parents will receive direct instruction on skills that have been found to be established strategies or approaches to promote skill acquisition, maintenance, and generalization for adolescents with ASD(Hume et al., 2014; National Autism Center, 2009; Wong et al., 2015). Direct instruction will be combined with practice utilizing these skills through role play. Parents will be taught to use a behavior contract (see Figure 3 for an example of a completed behavior contract) to target the adolescent practicing the specific DLS that are addressed in the intervention. The behavior contract, as it applies to each skill, will be reviewed each week and will be the primary method in which parents will hold adolescents accountable for working towards their DLS goals. The therapist in the parent group sessions will also discuss barriers (e.g., addressing

decreased motivation from teen to work on DLS, developing parental skills to foster independence with DLS, identifying rewards to increase the likelihood of continued skill development) and assist in problem-solving these barriers.

STRW Telehealth Sessions: The STRW parent sessions will be facilitated via video, using the HIPAA compliant version of Zoom. The format will be similar to the in-person sessions.

The STRW teen sessions will be scheduled and run by a psychology post-doctoral fellow or graduate student trainee. The sessions will be scheduled for 1 hour, and both parent and teen will participate. Targeted daily living skills will be practiced using the participant's home appliances and materials.

The PI will provide weekly supervision to all fellows and trainees that facilitate the STRW adolescent sessions. Both in-person and telehealth sessions will be videotaped and coded for treatment adherence and fidelity. A blinded coder will complete a treatment adherence and fidelity checklist on 25% of the sessions chosen at random.

PEERS Control Group:

Due to COVID-19, an undetermined number of sessions will be conducted via telehealth using a HIPAA approved version of Zoom.

PEERS In-Person Sessions: PEERS is the control group and consists of 14 weekly (90 minute) concurrent sessions that both adolescents with ASD and their parents attend. Social-communication and interaction skills such as building friendships, handling arguments, dealing with teasing, arranging and attending outings with peers are targeted through direct instruction, modeling, and practice in adolescent sessions. Parents are taught how to build and reinforce social skills outside of sessions. The purpose of the control group is to allow us to assess change in daily living skills in a group of high functioning adolescents with ASD who have deficient daily living skills but do not receive systematic behavioral treatment targeting specific skills using evidence based strategies.

PEERS Telehealth Sessions: The PEERS parent and teen sessions will be run simultaneously using the HIPAA compliant version of Zoom. This will require families to have two devices so both parent and teen can attend sessions at the same time.

DURATION:

The entire study will last from October 2018 through December 2022. Participant recruitment and randomization will begin in October 2018. The duration of the study per participant randomized to either STRW or the control group is approximately 12 months. Data collection will be completed by [name] and approved research personnel. Data analysis and reporting of results pertaining to the primary aims of the current study are expected to continue through December 2022.

DATA ANALYSIS/METHODS:

Data Entry Procedures

Physical data, including test protocols that are collected at CCHMC will be housed in locked file cabinets in the PI's lab space. This space will be locked at all times. Only the principal investigator or other IRB approved members of the CCHMC research team will have access to the physical data.

All data for each participant will be labeled with a unique ID number. Source documents and protocols may be scanned to a PDF and stored as an electronic file in the secured CCHMC server. Data will be entered into REDCap, a secure, web-based application designed to support data capture for research studies, providing: 1) an intuitive interface for validated data entry; 2) audit trails for tracking data manipulation and export procedures; 3) automated export procedures for seamless data downloads to common statistical packages; and 4) procedures for importing data from external sources.

After a family has completed participation, the physical files will be stored in locked cabinets at CCHMC. Audio and video recordings will be uploaded to a secure CCHMC server or external hard drive which only IRB approved staff will have access to. The hard drive will remain locked in a cabinet in staff office. Data in the electronic database are available indefinitely to qualified researchers who have access to the database. Thus, unless a participant indicates that they no longer consent to making their data available for analysis, de-identified electronic data will remain available for research in the database indefinitely. Audio recordings of parent interviews, video recordings of assessments, and video recordings of group sessions will be destroyed after data analysis has been completed and the study is closed. Physical data obtained from participants will also be housed by the PI indefinitely given that data collection has concluded. There may be reason to move the hard copy files to a different storage location at some point (e.g., P.I. change/move) either during or after the study. This will be approved through the IRB and all protected health information will remain secure. If at any time during or after the conclusion of the study, a participant requests that their data not be used, the PI will immediately destroy all physical data and also ensure that all electronic data connected to that participant be removed from the database.

Analyses

A secure REDCap⁸⁰ database has been built and will be maintained for all measures administered in the current study. The primary analysis will be conducted with an intent-to-treat approach. The primary outcome measures for Objectives 1 and 2 at post-treatment and 6-month follow-up are (1) change in Vineland-3 DLS domain raw score and age equivalent score and (2) change in score on the goals targeted on the DLS-GAS. We will also evaluate the Vineland-3 subdomain raw scores and age equivalent scores. The expectation is that the STRW group will have an increased change in score on both the Vineland-3 and DLS-GAS as compared to the control group. All analyses will be done using SPSS Version 20.0. Univariate statistics such as means, medians, and standard deviations will be computed for each variable to allow for examination of any outliers, variables that are not normally distributed, and heterogeneous variance between groups. The comparability of the two groups in some measured baseline covariates prior to treatment will be assessed using chi-square tests for categorical variables and t-tests for continuous variables. Variables found to be non-normal will be transformed using appropriate functions to confirm with the normality assumptions.

To test Aim 1: Initially a two-sample t-test will be used to test the difference on the change scores in the Vineland-3 DLS domain and GAS (post-treatment and baseline) between the STRW and control groups. Although this is a randomized study it is possible that some of the demographic variables might be differentially distributed between the groups. In this case, the initial analysis will be followed by a general linear regression analysis where cohort will be treated as the main effect and other differentially distributed variables will be added to the model as possible confounders in order to investigate the independent effect of the intervention group on outcome.

To test Aim 2: The within-subject change between post-treatment and 6-month follow-up for each individual receiving the intervention will be calculated and a paired t-test will be conducted to evaluate this change (post-treatment and 6-month follow-up).

To test Aim 3: Exploratory analyses will be conducted to examine the relationship between progress in DLS and executive functioning, social skills, and parenting and family factors. A regression analysis will be used to estimate and examine this potential relationship. In this model the change score (post-treatment and baseline) will be modeled as a function of each of the measures of executive function, social skills and parenting and family factors. This will allow us to characterize the response profile.

Missing data methods

All missing data will be discussed and every effort will occur to ensure all data are accounted for. Parents will be given multiple opportunities to fill out parent-report forms. To minimize possible loss to follow up, we will stay in close contact with families and identify any potential barriers to successful completion. Despite these efforts, missing data may occur. We will first examine the missing pattern to determine if missingness occurs systematically and differentially for each group, and tabulate the reason for missingness. Assuming at random, we will use multiple imputation technique to generate multiple datasets and systematically combine the estimates obtained from each dataset and associated variability. We will also investigate the potential that the missingness is not at random by performing sensitivity analysis recommended for clinical studies. Suspected biases will be taken into account in the interpretation of results.

Sample Size and Power Calculations

The pilot RCT is being conducted with the intent of examining the differences in DLS to be expected. Few studies have examined the trajectory of DLS in individuals with ASD(Baghdadli et al., 2012; Bal et al., 2015; Szatmari et al., 2009), and no studies have examined how DLS develop during adolescence. Power calculations focused on the anticipated increase or improvement in the age equivalence scores of each of the Vineland-3 DLS subdomains for the STRW group and control group. We used conservative estimates of change in DLS subdomain age equivalence scores for our sample size estimation, even though a recent pre-post trial on STRW with 7 participants found a mean improvement of 2.3 to 2.6 years across the 3 subdomains(Duncan et al., in press) from baseline to post-treatment.

Aim 1: For each DLS subdomain, we anticipate that adolescents in the STRW group will have a mean improvement of 9 months (a mean gain in age equivalence of 9 months) at post-treatment compared to a mean improvement of 4 months in the control group. Assuming a conservative pooled standard deviation of 8.4, we will have 80% power to detect the above effect size (of 0.71) with 32 participants per group. We will have 90% power to detect an effect size of 0.82 (a 9.9-month difference in the change of age equivalents between groups).

Aim 2: For each DLS subdomain, we anticipate that all participants, after receiving the STRW treatment, will maintain treatment gains from post-treatment to 6-month follow-up.

FACILITIES and PERFORMANCE SITES:

The Division of Behavioral Medicine and Clinical Psychology (BMCP) at Cincinnati Children's Hospital Medical Center (CCHMC) will serve as the project site for the recruitment and assessment of participants for the study. Assessment rooms (approximately 225 sq. ft.) within DDBP will be used for the assessments. The video and audio recording equipment needed for the project will be housed in this space for the duration of the project.

The in-person STRW and control group sessions will be held in the Schubert Research Clinic through the Clinical Translational Research Center (CTRC) in the T building on CCHMC's campus. We will use 2 conference rooms for the parent and adolescent weekly meetings. We will be using the Metabolic kitchen for the cooking portion of the STRW group.

POTENTIAL BENEFITS:

We hope that all participants in the intervention group will benefit greatly from the individualized intervention in daily living skills provided in this study. We also hope it may increase skills in other areas and by incorporating parental involvement, potentially directly affect current functioning and future adult outcomes by increasing capabilities for skills that are needed to succeed in college, employment, and independent living. Further potential benefits for those enrolled in the PEERS intervention include hopefully improving the participant's social skills. However, it is important to

emphasize that this study is being conducted for research purposes and does not ensure better or safer treatment nor guarantee individual benefits to the participant. Participants will receive monetary compensation for their time spent completing the study protocol.

A possible indirect benefit of this research is the knowledge that results from this project might positively impact the ability of researchers to obtain a better understanding of issues related to the postsecondary education, employment, and the overall transition to adulthood for individuals with DD. Further, this may lead to an increase in better services and supports as they make the transition to adulthood.

POTENTIAL RISKS, DISCOMFORTS, INCONVENIENCES AND PRECAUTIONS:

The risks associated with participating in the study are considered to be minimal and are commensurate with everyday risks. All of the measures used in this study have been used in previous research. Participants may experience transient emotional distress upon completing some of the interviews and questionnaires, which ask about their child's development or affective state. The clinicians and researchers who will be conducting the assessments are trained to assess and minimize any discomfort that results from the interviews or questionnaires. In the event that a participant finds the psychological evaluation mildly anxiety provoking, interviewers will express empathy and test-appropriate encouragement and reassurance. All participants will be informed that their participation is completely voluntary, and that they are free to withdraw from the study at any time.

The population of the study does include women capable of bearing children; however the study poses no additional risk to pregnant women.

RISK/BENEFIT ANALYSIS:

Based on the stated potential benefits and potential risk, we believe the study is considered "Minimal Risk", without potential direct benefit to the participants. Based on this assessment, we believe there is no need for a Data Safety Monitoring Board. The P.I. will be responsible for monitoring the study data through consistent communication with the coordinator during each phase. We will report any unanticipated problems and unexpected adverse events per CCHMC policy R-18.

PRIVACY & CONFIDENTIALITY:

Participants who indicate that they no longer wish to participate will not be contacted again for any reason.

Participants will be informed that all information they provide will be kept confidential unless there is a risk of harm to the participant or others (e.g., abuse, suicide, homicide), and/or if a clinician is required by law to make a report. Appropriate referrals will be provided in situations where follow-up clinical services are required.

Staff members will be trained on the importance of confidentiality and techniques to maintain confidentiality of all information reported by research participants. Detailed information related to data entry and storage procedures is detailed above in the Data Analysis/Methods section.

COST OF PARTICIPATION:

All procedures related to this study are for research purposes only. Families or third party payers will not be charged or billed for any part of the study procedures.

PAYMENT FOR PARTICIPATION:

Both adolescent and parent participants will each receive \$50 as compensation for the baseline assessment prior to randomization For both the post-group and 6-month follow-up assessments, parent participants will receive \$50 for compensation. For both the post-group and 6-month follow-up assessments, adolescents will receive \$25 for compensation. Parents will also receive another \$25 for each of the 12 month, 18 month, and 24 month calls, if they complete them. Parents will receive \$25 for the outcomes survey. Thus, adolescents will receive a total of \$100 and parent participants can receive a total of up to \$250 as compensation for participating in the assessment visits. Screen fails will receive \$25 for parent and teen for coming to the pre-assessment but not completing all the measures.

Participants will not be compensated for attending the daily living skills treatment sessions or the PEERS group sessions.

References

- Bal, V. H., Kim, S., Cheong, D., & Lord, C. (2015). Daily living skills in individuals with autism spectrum disorder from 2 to 21 years of age. *Autism*, *19*(7), 774-784. doi:10.1177/1362361315575840
- Barneveld, P. S., Swaab, H., van Engeland, H., & de Sonneville, L. (2014). Cross-sectional evidence for a decrease in cognitive function with age in children with autism spectrum disorders? *Autism Research*, 7(5), 527-534. doi:10.1002/aur.1380
- Becker, S. P. (2015). Child Concentration Inventory, Second Edition (CCI-2). Cincinnati, OH.

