In the current study, we will examine how the *Surviving and Thriving in the Real World (STRW)* intervention improves the DLS of 72 adolescents with ASD in their last 2 years of high school. Our previous work has found that STRW can increase the DLS of adolescents with ASD by 2-2.5 years over the course of the intervention, which has significant and practical implications for both current functioning (e.g., maintaining a part-time job while in high school, managing a checking and savings account, cooking meals for oneself) and future adult outcomes (e.g., budgeting for monthly expenses, keeping one's apartment clean, making routine medical appointments, planning for meals for an entire week and then going grocery shopping). The current study will examine these outcomes and also explore how factors such as social-communication skills (e.g., understanding expectations, taking others' perspectives), executive functioning abilities (e.g., getting started on tasks, organizing, managing time), and parenting and family factors (e.g., parental stress, over-involvement in daily routines) may affect one's ability to acquire DLS.

PURPOSE OF STUDY:

The main objective of the current proposal is to conduct a pilot RCT (i.e., treatment group and social skills control group) to examine how participation in STRW affects proximal outcomes with a larger sample size (n = 70). As social skills, executive functioning, and parenting factors have been linked to the acquisition of DLS, the current study will also explore how these are linked to participation in STRW. Lastly, goal attainment scaling (GAS) will be utilized, along with gold standard parent report and adolescent self-report measures, to assess DLS.

Aim 1: Examine the effectiveness of Surviving and Thriving in the Real World (STRW) in a pilot RCT. Participants will be randomized to STRW or a social skills control group (Program for the Evaluation and Enrichment of Relational Skills-PEERS). The STRW group will show significant improvement on the Vineland Adaptive Behavior Scales, 3rd Edition (Vineland-3) and progress on targeted DLS using goal attainment scaling (GAS), baseline to post-treatment, as compared to the control group.

Aim 2: Assess the maintenance of treatment gains 6-months after completion of STRW. Participants in the STRW group will continue to show significant improvement on the Vineland-3 and progress on targeted DLS using GAS, baseline to 6-month follow-up, as compared to the control group.

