
STUDY DESIGN:

Pilot RCT of Surviving and Thriving in the Real World (STRW): The pilot RCT will consist of running 5 cohorts of 16-20 high functioning adolescents with ASD (IQ≥70) and their parents in a

STRW treatment group or social skills control group. Once an eligible cohort of 16-20 adolescents with ASD has been recruited, adolescents will be randomly assigned to either the STRW group or control group using a stratified randomized block design with IQ as a strata variable (IQ<85 and IQ≥85) to ensure balanced group assignment for each cohort. Approximately 8-10 adolescents with ASD and their parents will participate in each STRW group. Thus, across 5 cohorts, the goal will be to enroll at least a total of 70 adolescents in the study, 35 in the STRW group and 35 in the control group across Years 1-3.

SELECTION AND RECRUITMENT OF PARTICIPANTS:

Inclusion Criteria

The inclusion criteria for the 70 adolescent participants include the following: between the ages of 15-22, in the last 2 years of high school (i.e., in the 11th or 12th grade or has deferred their high school graduation); a diagnosis of ASD (based on clinical judgement and/or meeting the cut-off score on the Autism Diagnostic Observation Schedule, 2nd Edition; ADOS-2)(Lord et al., 2012); a full scale IQ of 70 or above as measured by the Stanford Binet Intelligence Scales, 5th Edition (SB-5)(Roid, 2003); and deficient DLS as assessed by the Vineland Adaptive Behavior Scales, 3rd Edition(S. Sparrow, Cicchetti, & Saulnier, 2016) (Vineland-3; i.e., at least 1 of the 3 Daily Living Skills subdomains is at least 15 points below their full scale IQ).

Exclusion Criteria

Exclusion criteria include significant aggressive behaviors or mental health issues that require treatment out of the scope of the current intervention. Information about medication usage and services/therapies received at home, school, or community will be collected at each assessment. Also, if the adolescent has already completed the social skills group (PEERS), either at Cincinnati Children's or in another setting, they will not be eligible for the study unless it has been a significant amount of time since they did the PEERS group (2-3 years, or up to the discretion of the PI). In these cases, the parent must give verbal understanding that their child may be randomized to the social skills group.

Recruitment

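### Five cohorts of 16-20 give 80-100 participants, not the 70 (35 per arm) drawn from them or the 72 in the Abstract, so planned enrolment and its attrition allowance are not fixed

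*Combined protocol and SAP*

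**What the plan says.** The Study Design section describes "running 5 cohorts of 16-20 high functioning adolescents with ASD", together with their parents. It places randomisation after the cohort is complete: "Once an eligible cohort of 16-20 adolescents with ASD has been recruited, adolescents will be randomly assigned". On arm size it says: "Approximately 8-10 adolescents with ASD and their parents will participate in each STRW group". It then draws a total as a consequence of these figures: "across 5 cohorts, the goal will be to enroll at least a total of 70 adolescents in the study", divided as "35 in the STRW group and 35 in the control group across Years 1-3".

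The figure 70 recurs without the floor wording. Inclusion Criteria has "The inclusion criteria for the 70 adolescent participants include the following", and Purpose of Study has "affects proximal outcomes with a larger sample size (n = 70"). The Abstract differs: the study will examine how STRW "improves the DLS of 72 adolescents with ASD".

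The section on 12-, 18- and 24-month parent follow-up schedules visits for Cohorts 1 to 5, so five cohorts is not a slip confined to one sentence.

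Sample Size and Power Calculations uses another number: 80% power at an effect size of 0.71 with 32 per group, based on mean gains of 9 and 4 months and a pooled SD of 8.4. It also states 90% power at 0.82, with no separate group size. No dropout rate, alpha or sidedness is given, and no text connects 32 per group to 70, 72 or the cohort plan.

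**The concern.** The total of 70 is presented as the result of the cohort plan, but the cohort plan does not produce it. A reader finds 64, 70, 72 and 80-100 in one document, with nothing to say which is the planned enrolment or how the others derive from it.

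The total determines how many participants can be lost before the evaluable number falls below the 32 per group that the power statement needs. It also determines the power the trial has if few are lost. From 35 to 50 per arm, both change enough to matter for a trial whose results at post-treatment and 6 months depend on families staying in contact.

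**Working it through.** **Cohort arithmetic** (inputs from Study Design)

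- Total: 5 × 16 = 80 to 5 × 20 = 100.
- STRW arm: 5 × 8 = 40 to 5 × 10 = 50.
- Working back from 70: 70 / 5 = 14 per cohort, below 16; 35 / 5 = 7 per STRW group, below about 8-10.
- Working back from 72: 72 / 5 = 14.4 per cohort, also below 16.

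**Could something else close the gap?**

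- Screen failure: no. The 16-20 are already eligible when they are randomised.
- Dropout: 70 is a number to enrol, not to complete. Getting there from 80-100 would take 1 − 70/80 = 12.5% to 1 − 70/100 = 30% loss, and no rate is stated.
- Four cohorts: 4 × 18 = 72, and 70 lies between 4 × 16 = 64 and 4 × 20 = 80. Both totals would fit four cohorts, but that is inference, and the document says five in two places.

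**Reproducing the plan's power**

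The Analyses section names a two-sample t-test on change scores. Alpha and sidedness are not stated; I assume two-sided 0.05. With n per arm and standardised difference d, power comes from the noncentral t with 2n − 2 degrees of freedom and noncentrality d × √(n/2).

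- d = 0.71, n = 32: noncentrality 0.71 × √16 = 2.84; power 79.8% (normal approximation 81.1%). The stated 80% is reproduced.
- d = 0.82, n = 32: 89.8%. The stated 90% is reproduced, which supports the assumed alpha and sidedness.

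**What each total implies**

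The attrition allowance is 1 − 32/n, the loss per arm that still leaves 32. The power columns assume no loss.

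| Total | Per arm | Attrition allowance | Power, d = 0.71 | Power, d = 0.595 |
|---|---|---|---|---|
| 64 | 32 | 0% | 79.8% | 65.0% |
| 70 | 35 | 8.6% | 83.3% | 69.0% |
| 72 | 36 | 11.1% | 84.4% | 70.2% |
| 80 | 40 | 20% | 88.0% | 74.8% |
| 100 | 50 | 36% | 94.0% | 83.8% |

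The last column is needed because the power section's own inputs do not give its effect size: (9 − 4) / 8.4 = 0.595, assuming the SD is in months. Likewise 0.82 × 8.4 = 6.9 months, not the stated 9.9. At d = 0.595, 80% power needs 45.3, so 46 per arm.

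**The case against.** The best defence is that 70 is a minimum. Five cohorts of 16-20 satisfy it, 35 and 35 is simply the minimum split in two, and the STRW group size is itself approximate. That stands: enrolling 80-100 would not contradict the goal. It does not explain why 70 is offered as the consequence of the cohort figures, or why it appears elsewhere as a plain count.

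Three stronger readings are tempting, and the documents do not support them.

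- A reader might infer that the power is undefined. It is not: it is tied to 32 per group and reproduces, and every total in dispute exceeds 64. At the stated d = 0.71 the ambiguity changes the margin above 80%; before attrition it never takes power below that level.
- A reader might infer that enrolment is open-ended. It is bounded by five cohorts of at most 20 and by Years 1-3. No interim analysis or data-dependent stopping is described, so nothing here points to inflated type I error.
- A reader might take the sub-80% power figures as the result of the cohort mismatch. They come from the separate disagreement between 9 versus 4 months with SD 8.4 and the stated 0.71.

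The gap between 70 and 72 is also small in itself: one participant per arm and about one percentage point of power.

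**Conclusion.** The inconsistency is real and needs correcting, but it is a limited one. The step from the cohort plan to 70 fails, because the plan gives 80-100, and the Abstract adds an unreconciled 72. What is left open is the planned enrolment. The attrition allowance therefore ranges from 8.6% to 36% and, at d = 0.71, achieved power from 83% to 94% for 35 to 50 per arm. The power figures rest on two-sided 0.05, equal arms and no attrition; the first is an assumption that reproduces the stated 80% and 90%.

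The choice of total carries more weight once the effect size is corrected. At d = 0.595, the 46 per arm needed for 80% lies inside the 40-50 implied by the cohort plan and outside 35-36.

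**What to change.** State one planned total, and make the number of cohorts, the cohort size and the STRW group size agree with it in the Abstract, Purpose of Study, Study Design and Inclusion Criteria. Five cohorts of 16 would do this: 80 in total and 40 per arm, already within the cohort plan. If 70 is meant, the ranges of 16-20 and 8-10 must both change.

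Then state the attrition allowance that links the total to 32 per group (20% for 40 per arm), give alpha and sidedness, and restate power for that total. Reconcile the means, SD and effect size first, because the answer depends on them: at d = 0.595 power is 69% at 35 per arm, 75% at 40 and 84% at 50. If those inputs stand, the 32 per group must be revised as well, and with it the allowance.

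The cost is a text correction and one recalculation. A total of 80 adds no participants beyond what the cohort plan already describes.
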